5.2 Participant Registration

A written, signed, informed consent form (ICF) and a Health Insurance Portability and Accountability Act (HIPAA) authorization must be obtained before any study-specific assessments are initiated. A copy of the signed ICF will be given to the subject and a copy will be filed in the medical record. The original will be kept on file with the study records.

All participants consented to the study will be registered in OnCore®, the UCSF Helen Diller Family Comprehensive Cancer Center Clinical Trial Management System (CTMS). The system is password protected and meets HIPAA requirements.

A list of study subjects will be completed, and will include each subject's study number and initials. The investigator must also maintain a separate log of all the subjects screened for participation in the study but who will not participate, the reasons for their exclusion or non-participation, their initials, and the date on which the subject was excluded.

5.3 Schedule of Procedures and Assessments

5.3.1 Screening Assessments

The screening procedures and assessments must be completed within 12 weeks prior to the start of planned systemic therapy (sub-cohort A1) or within 24 weeks after the start of current systemic therapy (sub-cohort A2). *(Note: Patients in sub-cohort A1 who initiate systemic therapy during the screening period/prior to study enrollment may be re-consented to transition to sub-cohort A2.)*

- Baseline conditions
- Concomitant medications
- Demographic information (e.g. age, race, height, weight, and body mass index)
- ECOG or Karnofsky Performance status
- Laboratory procedures
 - Prostate-specific antigen
 - Complete blood count + differential
 - Lactate dehydrogenase
 - Liver function tests including AST, ALT, total bilirubin, and alkaline phosphatase

Additional screening assessments for sub-cohort A1:

- Baseline ^{68}Ga -PSMA-11 PET scan will be performed and reviewed to confirm the presence of at least one metastatic lesion with PSMA uptake at or above that of the blood pool. A ^{68}Ga -PSMA-11 PET scan performed prior to study entry may serve as the baseline PSMA PET scan if within 12 weeks of the start of systemic therapy.
- Cross-sectional imaging of the chest/abdomen/pelvis (CT or MRI; with IV contrast if medically permissible) within 12 weeks of baseline ^{68}Ga -PSMA-11 PET scan (including the same day as baseline PET). Cross-sectional imaging performed prior to study entry may serve as baseline imaging if within 12 weeks of the start of systemic therapy.

Additional screening assessments for sub-cohort A2:

- Baseline ^{68}Ga -PSMA-11 PET scan performed within 12 weeks prior to start of current systemic therapy will be reviewed to confirm the presence of at least one metastatic lesion with PSMA uptake at or above that of the blood pool
- Cross-sectional imaging of the chest/abdomen/pelvis (CT or MRI; with IV contrast if medically permissible) performed within 12 weeks of baseline ^{68}Ga -PSMA-11 PET scan (including the same day as baseline PET) will be reviewed

5.3.2 Baseline ^{68}Ga -PSMA-11 PET/MRI or PET/CT

- ^{68}Ga -PSMA-11 PET/CT or PET/MRI
 - Participants will begin PET imaging between 55 and 70 minutes after the injection of Ga-PSMA-11 at a dose of 3-7 mCi.
 - A dose of 20 mg of furosemide (Lasix) is recommended to be injected intravenously together with, shortly before, or after, administration of the radiotracer in order to minimize PET scatter artifacts from excreted radiotracer accumulation in the kidney and urinary bladder that can occur with the gallium-68 radionuclide. Furosemide should not be administered in patients with medical contraindications to Furosemide.
 - Contrast agent for MRI or CT will be administered as clinically indicated.
 - Participants will be monitored for adverse events for two hours after Ga-PSMA-11 administration.
 - A formal radiology report from the imaging scan will be generated by the Nuclear Medicine department. If any unexpected findings are visualized, these will be reported to the treating health care provider, who will then contact the patient if additional work-up needs to be performed.
 - If the patient has received a ^{68}Ga -PSMA-11 PET scan prior to study enrollment and within 12 weeks prior to the start of current systemic therapy (sub-cohort A2), the PET scan may serve as the baseline PET scan and does not need to be repeated at screening.

5.3.3 Baseline Tumor Biopsy and Circulating Tumor Nucleic Acid Collection (Optional – Within 12 weeks of Baseline PSMA PET)

Patients in sub-cohort A1 will undergo optional metastatic tumor biopsy and circulating tumor nucleic acid collection within 12 weeks of baseline PSMA PET scan. Biopsy and/or circulating nucleic acid collection will be performed under protocol CC # 155518. Soft tissue lesions with low/negative PSMA uptake will be prioritized for tissue acquisition. However, either bone or soft tissue lesions that are deemed safely accessible per Interventional Radiology assessment will be potentially considered for imaging.

Optional circulating tumor nucleic acid collection under companion protocol CC# 155518 will also be performed at the following times:

- Initiation of systemic treatment
- Disease progression

5.3.4 Baseline FDG PET (Optional for sub-cohort A1 only – within 12 weeks of Baseline PSMA PET)

Patients in sub-cohort A1 may undergo optional FDG PET/CT scan (within 12 weeks after date of baseline Ga-PSMA PET) per standard imaging procedures.

5.3.5 Initiation of Systemic Therapy

- Sub-cohort A1: Patients will subsequently initiate systemic treatment for castration resistant prostate cancer. Choice of therapy will be per discretion of the treating physician. Response monitoring with respect to serum PSA and conventional imaging will occur per standard of care and provider discretion. A minimum of three serum PSA values are required including at baseline within 12 weeks prior to initiation of systemic treatment, at 8 weeks (+/- 4 weeks), and at 16 weeks (+/- 8 weeks) from start of systemic therapy.
- Sub-cohort A2: Patients must be currently receiving systemic treatment for castration resistant prostate cancer, initiated within 12 weeks after their baseline 68Ga-PSMA -11 PET scan. Choice of therapy will be per discretion of the treating physician. Response monitoring with respect to serum PSA and conventional imaging will occur per standard of care and provider discretion. A minimum of two serum PSA values are required including at baseline within 12 weeks prior to initiation of systemic treatment and at 16 weeks (+/- 8 weeks) from start of systemic therapy.

5.3.6 Follow up ⁶⁸Ga-PSMA-11 PET (16 weeks +/- 8 weeks from date of systemic treatment initiation)

Patients will undergo repeat ⁶⁸Ga-PSMA-11 PET after 16 weeks (+/- 8 weeks) from date of initiation of systemic treatment.

The specific time frame for imaging will depend on the treatment modality administered, and will be standardized as follows:

- Androgen Receptor (AR) targeted therapy (20 weeks +/- 4 weeks)
- PSMA-targeting radioligand therapy (12 weeks +/- 4 weeks)
- Cytotoxic chemotherapy (12 weeks +/- 4 weeks)
- Immunotherapy (12 weeks +/- 4 weeks)

Patients with a negative baseline PSMA PET scan (i.e. no metastatic lesion with PSMA uptake at or above that of the blood pool) will not be eligible for the follow up PSMA PET.

Patients who underwent PET/CT at baseline should have same imaging modality performed during follow-up, and likewise patients who underwent PET/MR at baseline should have same imaging modality performed for follow up PSMA PET imaging.

5.3.7 Time of Disease Progression by PCWG3 Criteria (Optional)

Patients will undergo an optional third ⁶⁸Ga-PSMA-11 PET at the time of progression by PCWG3 criteria. Patients who underwent PET/CT at baseline should have same imaging modality performed during follow-up, and likewise patients who underwent PET/MR at baseline should have same imaging modality performed during follow up.

5.3.8 Long Term Survival Follow Up

Participants will be followed by telephone call and/or chart review every 3 months to record survival status until death, study withdrawal, or study closure, whichever occurs first.

5.4 Dietary Restrictions

None. No fasting is required for PSMA PET imaging.

5.5 Prohibited Medications

None. There are no prohibited medications.

6 Reporting and Documentation of Results

6.1 Evaluation of Safety

Analyses will be performed for all patients having received at least one dose of IMP. The study will use the Common Terminology Criteria for Adverse Events (CTCAE v5.0) criteria for reporting of non-hematologic adverse events and modified criteria for hematologic adverse events.

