6.2 Definitions of Adverse Events

6.2.1 Adverse Event

An adverse event (also known as an adverse experience) is defined as any untoward medical occurrence associated with the use of a drug in humans, whether or not considered drug related. More specifically, an adverse event (can be any unfavorable and unintended sign (e.g., an abnormal laboratory finding), symptom, or disease temporally associated with the use of a drug, without any judgment about causality. An adverse event can arise from any use of the drug (e.g., off-label use, use in combination with another drug) and from any route of administration, formulation, or dose, including an overdose.

Laboratory test value abnormalities will not be recorded as AEs unless they are designated as clinically significant, defined as any one of the following: symptomatic, requiring treatment, resulting in dose modification or delay or premature study withdrawal, or placing the subject at risk for other toxicity in the judgment of the treating investigator.

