6.2.4 Recording of Adverse Events

Refer to the Data Safety Monitoring Plan, located in Appendix 2.

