3.1 Adverse Event Monitoring

All Grade 3-5 adverse events (AEs), whether or not considered to be expected or unexpected and whether or not considered to be associated with the use of the investigational agent(s) or study procedure, will be entered into OnCore®, UCSF's Clinical Trial Management System.

Adverse events are graded according to the Common Terminology Criteria for Adverse Events (CTCAE) as developed and revised by the Common Therapy Evaluation Program (CTEP) of the National Cancer Institute. Adverse events are further given an assignment of attribution or relationship to investigational agent or study procedure. Attribution categories are:

- **Definite** – The adverse event is clearly related to the investigational agent(s) or study procedure.
- **Probable** – The adverse event is likely related to the investigational agent(s) or study procedure.
- **Possible** – The adverse event may be related to the investigational agent(s) or study procedure.
- **Unrelated** – the adverse event is clearly not related to the investigational agent(s) or study procedure.

All Grade 3-5 adverse events entered into OnCore® will be reviewed on a monthly basis at the Site Committee meetings. The Site Committee will review and discuss the selected toxicity, the toxicity grade, and attribution assignment.

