3.2 Serious Adverse Event Reporting

By definition, an adverse event is defined as a serious adverse event (SAE) according to the following criteria:

- Death.
- Life-threatening (i.e. results in an immediate risk of death).
- Requires inpatient hospitalization or prolongation of existing hospitalization,
- Permanent or significant disability/incapacity
- Gives rise to a congenital anomaly/birth defect, or cancer, or any experience that suggests a significant hazard, contraindication, side effect, or precaution that may require medical or surgical intervention to prevent one of the outcomes listed above.
- Event occurring in a gene therapy study.
- Event that changes the risk/benefit ratio of a study.
- Any other event the Principal Investigator judges to be serious or which would suggest a significant hazard, contraindication, side effect, or precaution.

Serious adverse event reporting will be in accordance with all IRB regulations. For trials conducted under an investigational new drug (IND) application, the SAE will be reported in accordance with Code of Federal Regulation Title 21 Part 312.32 and will be reported on a Med Watch form.

UCSF IRB website for guidance in reporting serious adverse events:
<https://irb.ucsf.edu/adverse-event>

Med Watch forms and information:

www.fda.gov/medwatch/getforms.htm

All serious adverse events are entered into OnCore®, as well as submitted to the IRB (per IRB guidelines). The SAEs are reviewed and monitored by the Data and Safety Monitoring Committee on an ongoing basis and discussed at DSMC meetings, which take place every six weeks. The date the SAE is sent to all required reporting agencies will be documented in OnCore®.

If the SAE involves a subject death, and is determined to be possibly, probably or definitely related to the investigational drug or any research related procedure, the event must be reported to the DSMC Chair (or Vice Chair) and DSMC Director within one business day.

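### The entry rule does not require non-serious Grade 1-2 tracer reactions, so the section 6.1 safety analysis could miss reactions seen in the two-hour observation

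*Combined protocol and SAP*

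**What the plan says.** Section 6.1 sets the safety population without a grade limit: "Analyses will be performed for all patients having received at least one dose of IMP". It names CTCAE v5.0 "criteria for reporting of non-hematologic adverse events and modified criteria for hematologic adverse events". The modified criteria are not described anywhere in the documents.

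Section 6.2.1 defines an adverse event with no severity floor. Its one exclusion concerns laboratory values: "Laboratory test value abnormalities will not be recorded as AEs unless they are designated as clinically significant".

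Section 5.3.2, on the baseline scan, states: "Participants will be monitored for adverse events for two hours after Ga-PSMA-11 administration". Sections 5.3.6 (follow-up scan) and 5.3.7 (progression scan) do not repeat this.

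Section 6.2.4, on recording, contains only a pointer: "Refer to the Data Safety Monitoring Plan, located in Appendix 2". Section 6.2.6, on monitoring, does the same.

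Appendix 2, section 3.1, gives the entry rule for OnCore: "All Grade 3-5 adverse events (AEs), whether or not considered to be expected or unexpected", and regardless of relation to the agent or procedure. The same section assigns each adverse event an attribution from definite to unrelated. It also grades events by CTCAE, naming no version and making no exception for hematologic events. Appendix 2, section 3.2, adds entry of serious adverse events, with no grade limit.

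**The concern.** The agent under study is the tracer, and the two-hour observation is the only adverse-event check that the protocol ties to an injection. Reactions seen in such a window may well be mild and non-serious, and that is the class for which no entry is required. The protocol therefore looks for these events and plans a safety analysis of everyone dosed, but has no rule that carries the one to the other.

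At stake is the safety description of the imaging agent. A report built on the required data could say that no tracer reactions occurred when staff had seen some, and a reader could not tell that from a true absence.

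The two statements on hematologic grading are a separate inconsistency. They do not cause the loss of mild reactions.

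**Working it through.** **Following one event through the text.** Take a non-serious Grade 1 or 2 reaction seen within two hours of a baseline injection.

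1. It is an adverse event under 6.2.1, and it falls in the observation that 5.3.2 describes.
2. For recording, 6.2.4 sends the reader to Appendix 2.
3. It is below Grade 3, so section 3.1 there does not require entry.
4. It is not serious, so section 3.2 does not require entry either.
5. The monthly Site Committee review covers the Grade 3-5 events already entered, so it would not reveal the omission.
6. Two general clauses remain. Section 8.6 enters study data by case report form in line with the study calendar, but the calendars in 5.1.1 and 5.1.2 have no adverse-event row. Section 7.4.1 includes data from dosed subjects where appropriate, which governs data in hand and creates no duty to record.

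So the event need not reach the 6.1 analysis.

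**Size.** The plan gives no figure on this point to reproduce. Inputs:

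- Number of observed injections, n. The documents do not give the split between sub-cohorts A1 and A2. Assume half of the 100 evaluable patients are A1. A2 baseline scans predate enrolment, so the stated observation covers at most about n = 50 on-study injections. It covers fewer if some A1 baseline scans also predate study entry, which 5.3.1 allows.
- Rate of non-serious Grade 1-2 reactions per injection, p. Not given; assumed 1%, 2% and 5%.

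Expected number = n × p. Chance of at least one = 1 − (1 − p)^n, taking injections as independent. For n = 50:

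| p | Expected | Chance of at least one |
|---|---|---|
| 1% | 50 × 0.01 = 0.5 | 1 − 0.99^50 = 1 − 0.60501 = 39% |
| 2% | 50 × 0.02 = 1 | 1 − 0.98^50 = 1 − 0.36417 = 64% |
| 5% | 50 × 0.05 = 2.5 | 1 − 0.95^50 = 1 − 0.07694 = 92% |

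Sensitivity to n: with n = 25 the chances are 1 − 0.99^25 = 22%, 1 − 0.98^25 = 40% and 1 − 0.95^25 = 72%. With n = 100 they are 63%, 87% and 99%.

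**What a nil report would mean.** If every reaction were recorded, none in 50 would give an upper 95% bound of about 3/50 = 6% (rule of three). Under the present rule, no entered mild reactions is compatible with any rate, because none has to be entered.

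**Hematologic grading.** Section 6.1 applies unspecified modified criteria; Appendix 2 applies CTCAE to adverse events generally. A hematologic event cannot be graded both ways if the two differ, and grade is one trigger for entry. But both calendars schedule the blood count only at screening, and 6.2.1 leaves out laboratory changes that are not clinically significant. Few events are likely to turn on the conflict.

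**The case against.** The strongest reply is that Appendix 2 sets a minimum. It does not forbid entering mild events, section 8.6 says the case report forms will document safety, and those forms are not in the documents. This stands as a limit: the defect is that entry is not required, not that mild events will certainly be lost.

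It is also fair to say that the stakes are modest. Safety is not a primary, secondary or exploratory objective, and 7.4 describes no specific safety table. That stands too; the primary analysis is untouched.

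Four stronger readings are tempting, and the documents do not support them:

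- **Only Grade 3-5 events are recorded.** Appendix 2, section 3.2, also enters serious events of any grade. It counts as serious any event that the Principal Investigator judges to be serious or to suggest a significant side effect or hazard. The gap is confined to non-serious Grade 1-2 events.
- **Every injection is observed.** A reader might count two injections per A1 patient and one per A2 patient (50 × 2 + 50 × 1 = 150 under an even split) and conclude that a nil report would give a bound of 3/150 = 2%, ruling out a 5% rate. The observation is stated for the baseline scan only. With at most about 50, the bound is 6% and does not rule out 5%.
- **Systemic-therapy toxicity would swamp the tables.** Grade 3-5 events of any cause are entered with no stated end date, but attribution is already assigned, so tracer-related events among those entered can be separated. Attribution cannot recover events that were never entered.
- **The 30 days in 6.2.7 give a ready safety window.** That period concerns notification of related deaths and says nothing about other events.

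**Conclusion.** The point holds in a limited form. Under the stated rules, non-serious Grade 1-2 tracer reactions seen in the two-hour observation need not be entered, so the 6.1 analysis could show none when some were seen. With about 50 observed baseline injections and a true rate of 1% to 5%, the chance that at least one such reaction occurs is between 39% and 92%. Both the count and the rates are assumptions.

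The conclusion that entry is not required rests on the text alone and does not depend on those figures. Whether mild events would in practice be lost depends on case report forms that cannot be seen here.

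The grading conflict is real, but it is a separate drafting matter of little practical weight.

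**What to change.** 1. In 6.2.4 or Appendix 2, section 3.1, require entry of adverse events of all grades seen during the stated post-injection observation.
2. State whether that observation also covers the follow-up and progression scans. The text now says so only for baseline.
3. In 6.1, tabulate events by the attribution already collected. For reactions in the observation period, use the observed on-study injections as the denominator.
4. If the sponsor keeps the present entry rule, 6.1 should say that its analysis is limited to Grade 3-5 and serious events and cannot support a statement that no mild tracer reactions occurred.
5. Separately, reconcile 6.1 and Appendix 2 to one defined grading system and version. Whether the modified criteria are to be defined or removed is for the sponsor to decide.

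The cost is protocol wording, one short form per observed injection, and a few mild events to enter. For the baseline scan, no new procedure is needed because the observation is already stated. If the sponsor decides that it covers later scans too, any added work there follows from that decision.

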6.2 Definitions of Adverse Events

6.2.1 Adverse Event

An adverse event (also known as an adverse experience) is defined as any untoward medical occurrence associated with the use of a drug in humans, whether or not considered drug related. More specifically, an adverse event (can be any unfavorable and unintended sign (e.g., an abnormal laboratory finding), symptom, or disease temporally associated with the use of a drug, without any judgment about causality. An adverse event can arise from any use of the drug (e.g., off-label use, use in combination with another drug) and from any route of administration, formulation, or dose, including an overdose.

Laboratory test value abnormalities will not be recorded as AEs unless they are designated as clinically significant, defined as any one of the following: symptomatic, requiring treatment, resulting in dose modification or delay or premature study withdrawal, or placing the subject at risk for other toxicity in the judgment of the treating investigator.

6.2.2 Adverse Reaction

An adverse reaction is defined as any adverse event caused by the use of a drug. Adverse reactions are a subset of all suspected adverse reactions for which there is reason to conclude that the drug caused the event.

6.2.3 Suspected Adverse Reaction

A suspected adverse reaction is defined as any adverse event for which there is a reasonable possibility that the drug caused the adverse event. For the purposes of investigational new drug (IND) safety reporting, “reasonable possibility” indicates that there is evidence to suggest a causal relationship between the drug and the adverse event. A suspected adverse reaction implies a lesser degree of certainty about causality than an adverse reaction.

6.2.3.1 Unexpected

An adverse event or suspected adverse reaction is considered *unexpected* if it is not listed in the investigator brochure or package insert(s), or is not listed at the specificity or severity that has been observed, or, if an investigator brochure is not required or available, is not consistent with the risk information described in the general investigational plan or elsewhere in the current application.

“Unexpected,” as used in this definition, also refers to adverse events or suspected adverse reactions that are mentioned in the investigator brochure as occurring with a class of drugs or as anticipated from the pharmacological properties of the drug, but are not specifically mentioned as occurring with the particular drug under investigation.

Adverse events that would be anticipated to occur as part of the disease process are considered *unexpected* for the purposes of reporting because they would not be listed in the investigator brochure. For example, a certain number of non-acute deaths in a cancer trial would be anticipated as an outcome of the underlying disease, but such deaths would generally not be listed as a suspected adverse reaction in the investigator brochure.

Some adverse events are listed in the Investigator Brochure as occurring with the same class of drugs, or as anticipated from the pharmacological properties of the drug, even though they have not been observed with the drug under investigation. Such events would be considered *unexpected* until they have been observed with the drug under investigation. For example, although angioedema is anticipated to occur in some participants exposed to drugs in the angiotensin-converting enzyme inhibitor class and angioedema would be described in the investigator brochure as a class effect, the first case of angioedema observed with the drug under investigation should be considered *unexpected* for reporting purposes.

